# 8.12 Laboratory Evaluations

# 8.12.1 Clinical Laboratory Evaluations

# Pregnancy Test

In order to rule out pregnancy, female participants with potential to become pregnantF will be testedCAL MEDICINE with a qualitative human chorionic gonadotropin (hCG) test on a urine sample Such testing will be iversity

APPROVE

done on Screening (S1)/ Vaccination (D0) day, before vaccination. If Day S1 and D0 vaccination are conducted separately, the urine pregnancy test must be repeated on visit Day 0 prior to vaccination. No injection of study product may be given to a woman with child-bearing potential without a negative pregnancy test being done or to any woman with a positive pregnancy test.

# 8.12.2 Immunological Assays

Immunogenicity testing will be performed by the laboratory at the Vaccine Trial Centre (VTC) using validated assays performed with established protocols. Samples may be sent to an additional qualified international lab for additional testing of influenza antibodies, as needed.

Hemagglutination Inhibition Assay (HI assay)

The HI assay is the most frequently used serologic test for determining immunologic response to influenza vaccination. Serum specific antibody against each of the vaccine strains represented in the vaccine will be measured by HI assay, which has been validated.

The two serological criteria that are accepted as indicators that the vaccine induces antihemagglutinin antibodies in subjects reaching levels required to meet current definitions of seroconversion:

• Percentage of subjects with either a pre-vaccination HI titer <1:10 and post-vaccination titer  $\geq$ 1:40 or pre-vaccination titer  $\geq$ 1:10 and a minimum 4-fold increase in post vaccination titer

• Increase in geometric mean titer (GMT) of serum HI antibodies

These two parameters are also evaluated yearly in human clinical trials due to the annual update of seasonal influenza vaccine strain composition.

http://ecdc.europa.eu/en/healthtopics/seasonal\_influenza/vaccines/Pages/influenza\_vaccination. aspx

# 8.12.3 Preparation, Processing and Transport Specimens

# **Blood collection**

Throughout the study, 9 ml of blood will be drawn from each participant.

Day 0: prior to immunization, 3mlblood sample will be drawn for immune responses (HI Assay).

Day 21 and Day 90: 3 ml of blood sample will be drawn for immune responses (HI Assay) on Day 21 and 3 ml of blood will be drawn for HI assay on Day 90.

The blood that is left over after testing as specified in this study protocol may be used in the future for other immune response tests which are related to this vaccine and will not be used for commercial purposes. The remaining blood will be stored at the Faculty of Tropical Medicine, Mahidol University for 5 years, after that the left over specimen will be destroyed per Destruction of Infectious Material Guideline.

# Serum processing

Serum samples will be separated from participant's blood specimens using centrifugation method. All serum samples will be stored at -20°C until used.

ETHICS COMMITTEE FACULTY OF TROPICAL MEDICINE MAHIDOL UNIVERSITY Hemagglutination inhibition assay (HI): Serum specific antibody against the vaccine strains (A/Michigan/45/2015 (H1N1)-pdm09, A/Hong Kong/4801/2014 (H3N2) and B/Brisbane/60/2008) will be determined using hemagglutination inhibition (HI) assay. Briefly, nonspecific inhibitors will be removed from serum by overnight treatment with receptor-destroying enzyme (RDE). RDE treated serum samples will then be serially 2-fold diluted in 96-well-V bottom plates starting at a dilution of 1:10, and 4 HA units of virus will be added. Control wells will receive phosphate-buffered saline (PBS) alone or PBS with virus in the absence of antibody. Following 30 min of incubation at room temperature, 50 ul of a 0.5% (v/v) of goose (for A/Michigan/45/2015 (H1N1)-pdm09 and B/Brisbane/60/2008)) and 0.75% Guinea pig (for A/Hong Kong/4801/2014 (H3N2)) erythrocytes will be added. The antibody, virus and erythrocytes will be gently mixed, and the results will be recorded after an incubation for 45-60 min at room temperature. HI titers will be recorded as the inverse of the highest antibody dilution that inhibited hemagglutination.

#### ILI investigations:

Nasal swab samples will be collected from subjects with ILI symptoms for the determination of influenza virus by polymerase chain reaction (PCR). Influenza subtypes will be further investigated by sequencing.

#### 9. Safety Oversight

#### 9.1 Data Safety Monitoring Board (DSMB)

The DSMB will monitor accumulating safety data from the trial, as well as aspects of trial conduct and criteria for altering its course on the basis of safety. Specifically, the DSMB has the responsibility to review safety and immunogenicity of the interventions during the trial. DSMB will make recommendations to the sponsor regarding subject safety and termination of the trial for toxicity. There will be DSMB meetings before initiation of the trial, after vaccination 50% of the participants and at the closeout. If either the DSMB Chair or the sponsor sees the need to call unscheduled meetings, then both parties will discuss the rationale and outcomes desired and call such a meeting.

#### 9.2 Expedited Safety Review

Safety events listed below require expedited Safety Medical Team (SMT) review within 36 hours of submission of the safety information to data management and or SAE reporting system.

Event and relationship to study agent as assessed	Severity Grade
by investigator	
SAE, related	All grades
Unsolicited AE, related	4
Local reactions – erythema or induration	4

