## 8.2 Solicited Local and Systemic Adverse Events

Solicited adverse events are pre-specified local and systemic adverse events that are common or known to be associated with vaccination and that are actively monitored as indicators of vaccine reactogenicity. Investigators will not be required to assess causality of solicited adverse events if the onset is during the solicitation periods. If a solicited adverse event progresses beyond the solicited period, it will continue to be reported as a solicited adverse event. If the solicited adverse event occurs after the solicitation period, it will be reported as unsolicited AEs.

For this trial, solicited local and systemic AEs will be assessed by study staff 30 minutes after vaccination then daily for three days by the participants. Participants will be provided with a thermometer, ruler, and diary card to record the presence or absence of solicited AEs, severity of the solicited AE, and use of concomitant medication. The severity of the solicited local and systemic adverse events will be graded using the Toxicity Table for Grading Adverse Events (Appendix A). The specific solicited local and systemic adverse events that will be reported for this trial are:

Solicited local adverse event (at site of injection):

- Erythema/redness—based on size in cm.
- Swelling/induration (hardness at site of injection)—based on size in cm.
- Pain (pain with or without touching the injection site).
- Limitation of arm movement

Systemic Reactions:

- Fever—taken orally by thermometer
- Fatigue/malaise
- Generalized muscle aches
- Joint aches
- Chills
- Nausea
- Headache

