# 8.3 Unsolicited Adverse Events

Unsolicited adverse events are any AEs that occur any time after the vaccine/comparator is given (temporally related to study product), whether or not deemed "related" to the product, and are not solicited (specifically asked of the participant). Unsolicited AEs can be observed by study staff while the participant is at a clinic for a study visit or reported by the participant at any time. Any sign or symptom that would normally be considered a "solicited AE" (for example, fever, nausea, injection site pain) starting after three days post-vaccination will be recorded as an unsolicited AE.

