#### 8.4 Serious Adverse Events

A serious adverse experience is any adverse experience occurring at any dose that

- † Results in death; or

ETHICS COMMITTEE FACULTY OF TROPICAL MEDICINE MAHIDOL UNIVERSITY

APPROVED

- † Is life threatening (places the subject, in the view of the investigator, at immediate risk of death from the experience as it occurred [Note: This does not include an adverse experience that, had it occurred in a more severe form, might have caused death]; or
- † Results in a persistent or significant disability/incapacity (substantial disruption of one's ability to conduct normal life functions); or
- † Results in or prolongs an existing inpatient hospitalization (hospitalization in defined as an
   impatient admission, regardless of length of stay, even if the hospitalization is a precautionary
   measure for continued observation) (Note: Hospitalization [including hospitalization for an
   elective procedure] for a preexisting condition which has not worsened does not constitute a
   serious adverse experience); or
- † Is a congenital anomaly/birth defect (in offspring of subject taking the product regardless of time to diagnosis); or
- † Is a cancer; or
- † Is an overdose (whether accidental or intentional). Any overdose whether or not associated with an adverse experience must be reported within 24 hours to The Government Pharmaceutical Organization following appendix B. Standard Operating Procedure Reporting of Serious Adverse Event, and to WHO focal point

Also: Other important medical events that may not result in death, not be life threatening, or not require hospitalization may be considered a serious adverse experience when, based upon appropriate medical judgment, the event may jeopardize the participant and may require medical or surgical intervention to prevent one of the outcomes listed previously (designated above by a †).

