# 8.5 AE/SAE Reporting Period and Parameter

Safety events are reported from the time of study injection (Day 0) through completion of the study at Day 90. Specifically, solicited AEs to assess local and systemic reactogenicities will be collected at 30 minutes and then daily for 3 days thereafter. If a solicited AE started during the 3 days post-vaccination and continues beyond the 3 days it will continue to be reported as a solicited AE. Unsolicited AEs and SAEs will be reported from Day 0 through the end of the study at Day 90.

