# 8.6 Severity of Adverse Events

An investigator who is a qualified physician, will evaluate all adverse experiences as to:

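### The 9.2 expedited-review table has no row for solicited systemic reactions, so a non-serious grade 4 reaction starting on Day 0-3, most clearly an oral temperature of 40.0 °C or more, has no required expedited SMT review.

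*Protocol*

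**What the plan says.** Protocol section 9.2 opens its table with "Safety events listed below require expedited Safety Medical Team (SMT) review within 36 hours"; the clock runs from submission of the information to data management or the SAE reporting system, not from onset. The three rows are:

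- related SAE, all grades;
- "Unsolicited AE, related", grade 4;
- "Local reactions – erythema or induration", grade 4, with no causality condition.

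Fever is on the list of solicited systemic events (sections 3 and 8.2) and is measured orally. Under section 8.3, a symptom of solicited type "starting after three days post-vaccination will be recorded as an unsolicited AE". Under section 8.5, an event that began in the window and "continues beyond the 3 days it will continue to be reported as a solicited AE". Section 8.2 adds: "Investigators will not be required to assess causality of solicited adverse events if the onset is during the solicitation periods".

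On grading, section 8.2 sends all solicited events to Appendix A. There, non-axillary fever of 40.0 °C or more is grade 4. SAP tables TREF 3.1 and 3.2 carry a grade 4 temperature row. Section 8.6 refers temperature grading to Appendix A but then prints labels that run only from 0 to 3.

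**The concern.** The obligation to escalate is missing in the window where a vaccine cause is most plausible. A grade 4 fever starting on Day 4 and judged related must go to the SMT on a 36-hour clock. If the fever starts on Day 1 and is not judged serious, the plan requires no expedited SMT review. The erythema and induration row shows that the authors did want some solicited reactions to reach the SMT on grade alone, but they wrote only a local row.

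What is at stake is the speed and certainty of escalation for a single severe systemic reaction. Immunogenicity endpoints, margins and analysis sets are not involved.

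**Working it through.** **Step 1. Trace one case through the rules.** Take an oral temperature of 40.0 °C or more with onset on Day 1, not judged serious.

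| Rule | Condition | Met? |
|---|---|---|
| 9.2 row 1 | SAE, related | No: not serious |
| 9.2 row 2 | Unsolicited, related, grade 4 | No: solicited by onset (8.2, 8.3, 8.5) |
| 9.2 row 3 | Local erythema or induration, grade 4 | No: systemic |
| Appendix B SOP, 6.1-6.3 | SAE notified to the SMT | No: not serious |
| Appendix B SOP, 6.10 | Six other reportable events | No: fever is not listed |
| Stopping rules 1 and 2 | One related SAE; one related grade 4 injection site reaction | No |
| Stopping rule 3 | Ten subjects with related grade 3 or greater reactogenicity | Not by one case |
| Stopping rule 4 | Five subjects with the same grade 3 or greater abnormality | Not by one case |

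None of the three rows applies. Move onset to Day 4 and row 2 applies, provided the investigator judges the fever related.

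**Step 2. Is there a grade 4 to escalate?**

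- *Fever.* Appendix A sets grade 4 by temperature alone, and the SAP tabulates grade 4 at 30 minutes and on Days 1-3. The printed labels in 8.6 stop at 3. Appendix A and the SAP together make fever the best-supported case.
- *Headache and fatigue.* Appendix A defines a grade 4 for both, but 8.6 and SAP TREF 3.10 and 3.12 score them 0-3. Many events meeting the Appendix A definition would be SAEs in any case; the headache definition, for example, includes an indication for hospitalisation.

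**Step 3. Is a grade 4 fever automatically an SAE?** The general grade 4 in 8.6 means immediate risk of death, which closely matches the life-threatening criterion in 8.4. A temperature reading alone does not establish that. Section 8.4 also admits "Other important medical events that may not result in death, not be life threatening", but by medical judgement. So a non-serious grade 4 fever is possible under the text.

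**Step 4. Frequency.** The documents give no rate of grade 4 fever. Section 2.4 reports no fever in 200 vaccine and 100 placebo recipients. With zero events, the one-sided 95% upper bound is 1 − 0.05^(1/n):

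- n = 200: 1.49%;
- n = 300: 0.99%.

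These bound fever of any grade and do not locate a grade 4 rate. The figures below are therefore illustrations under assumed rates p. They use n = 945 with equal rates in both arms, because the rules count subjects in a blinded trial.

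P(at least one) = 1 − (1 − p)^945:

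| Assumed rate of non-serious grade 4 fever | At least one case |
|---|---|
| 0.01% | 9% |
| 0.05% | 38% |
| 0.1% | 61% |
| 0.2% | 85% |

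**Step 5. How far do the aggregate rules help?** Let X be binomial (945, p), with every event treated as vaccine related. Rule 3 is not reached with probability P(X ≤ 9), and rule 4 with probability P(X ≤ 4).

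| Assumed total rate | Rule 3 not reached (all grade 3+ reactogenicity) | Rule 4 not reached (grade 3+ fever) |
|---|---|---|
| 0.2% | – | 96% |
| 0.5% | 98% | 49% |
| 1% | 53% | 4% |
| 2% | 1% | – |

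The two columns count different events, so one row does not describe one trial. The 0.2% entry for rule 4 corresponds to grade 4 fever at 0.2% with no grade 3 fevers at all. Any grade 3 fevers move the trial down that column.

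**The case against.** The strongest case is that the scheme is coherent as it stands. Related SAEs and selected grade 4 events escalate singly, and reactogenicity escalates in aggregate. The vaccine class has a well-established safety profile (section 4.2), and nothing in the plan promises expedited SMT review of solicited systemic reactions, so no text is contradicted. The uncovered event is narrow: a grade 4 fever judged neither life-threatening nor medically important, in someone not hospitalised. A fever noted only on the diary card is reviewed at Day 7 (-3, +7), so a new row would gain little time. Participants needing medical care are already told to inform the investigator as soon as possible (section 7.3).

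Most of this stands and keeps the point small. It does not explain why the same fever, if related, must be escalated from Day 4 but not from Day 1.

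A reader might infer more than the documents support:

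- *That an early severe fever escapes safety review.* It does not: "An investigator who is a qualified physician, will evaluate all adverse experiences" (8.6). Staff review the diary and take vital signs at Day 7 (7.4.1), the DSMB monitors accumulating safety data and may hold unscheduled meetings (9.1), and the sponsor may suspend the trial (9.3).
- *That the solicited or unsolicited label alone decides.* The unsolicited row also needs a judgement of relatedness.
- *That a serious solicited fever could be missed because 8.2 waives causality.* Section 10.2 requires every SAE to be reported whether or not related, and the Appendix B SOP sends SAE notifications to the SMT and requires causality assessment in all cases.

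**Conclusion.** The point holds as a minor gap in safety oversight. As written, a non-serious grade 4 solicited systemic reaction with onset on Day 0-3 has no required expedited SMT review. Fever of 40.0 °C or more is the best-supported instance. Extending the point with equal force to headache and fatigue is tempting but not supported, because 8.6 and the SAP score them 0-3.

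The conclusion rests on two readings: that Appendix A governs fever grade over the printed 0-3 labels in 8.6, and that a temperature value alone does not make an event serious. Its size cannot be put as a rate. The illustrations show only that one case is plausible in a trial of 945 if the true rate approaches 0.1%, and that rules 3 and 4 increasingly pause the trial once grade 3 or greater events reach about 0.5% to 1%. They treat every event as related, although 8.2 does not require that judgement. No endpoint, analysis set or non-inferiority conclusion changes.

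**What to change.** Add one row to the 9.2 table: *Solicited systemic reaction, grade 4 per Appendix A (including oral temperature of 40.0 °C or more), regardless of causality.* Causality should not be a condition, because investigators need not assess it for these events. Naming the temperature settles the grading question left by 8.6. Any pause decision after the review stays with the SMT and sponsor under 9.3.

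The row uses the existing SMT route and costs a few more expedited reviews. Its benefit is greatest for events seen at the 30-minute observation or reported because care was needed. For an event recorded only on the diary card, the SMT would hear only after the card review, between Day 4 (7 − 3) and Day 14 (7 + 7).

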#### 9.3 Study Safety Pause

During the expedited safety reviews, if the SMT identifies safety concerns that warrant a safety pause, the SMT will notify the sponsor. If a decision is made to pause the study all enrolment will MITTEE be held, pending consultation with the sponsor and or THAI FDA.

2112

GPO retains the right to temporarily suspend or prematurely discontinue this study at any time related to safety. If the study is stopped or suspended prematurely, GPO will inform the local principal investigators as well as regulatory authorities about the decision and the reasons for termination or suspension. If such action is taken, all efforts must be made to ensure the safety of the participants enrolled in the study. The principal investigators will assist GPO in informing the responsible Institutional Review Board (IRB)/ethics committee and provide the reason for the suspension or termination. In case of premature study or study clinic closure, the monitor will conduct all activities as indicated in the close out monitoring visit.

#### **Stopping rules:**

The occurrence of one or more of the following criteria will automatically pause or halt further vaccinations in the study:

- 1. One or more subjects experience a serious adverse event (SAE) that is suspected to be vaccine related.
- 2. One or more subjects experience a grade 4 injection site reaction (such as necrosis or sterile abscess at injection site requiring surgical intervention) that is suspected to be vaccine related.
- 3. Ten or more subjects experience a grade 3 or greater reactogenicity event following vaccination that is suspected to be vaccine related.
- 4. Five or more subjects experience the same grade 3 or more clinical abnormality following vaccination that is expected to be vaccine related

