# 7.4 Follow-up visits

# 7.4.1 Day 7(-3, +7 days) after Injection: Return the diary card

Subjects will return to the clinic on day 7 to return the diary card and report any adverse events. Subjects will be asked to report any adverse events that occur during the first seven days after immunization. Concomitant medication information will be collected.

At this visit;

- 1. Study staff will confirm participant identity.
- 2. Study staff will review the participant diary card and interim history with the participant and inquire about any new medical events since medical histories were last updated. Any AEs that have occurred and meeting reporting intensity will be recorded in the appropriate section(s) of the CRF. Diary card information will be entered into the CRF.
- 3. The participant will have temperature, pulse rate, and blood pressure recorded. A study clinician will perform a targeted (symptom based) physical examination and record the information on the CRF. Results will be reviewed by study staff and with the participant.
- 4. The participant will be instructed to inform the investigator as soon as possible if he/she experiences an AE requiring medical care and to seek medical care as appropriate. If the participant visits a health care provider, the participant should be sure to inform the health care provider of participation in this study and give the health care provider the contact information for the investigator.
- 5. There are no scheduled visits at week 2 after vaccination. Participants may be asked to come to the study clinic if the investigator follows up on any clinical issue. The participant will inform the study clinic of any medical events and seek medical care as needed. The participant will be instructed to give any health care provide they see the contact information for the investigator. FACULTY OF TROPICAL MEDICINE วิตยาลัยม

MAHIDOL UNIVERSITY

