# **11.4 Analysis of Safety Endpoints**

The safety profile of the GPO Tri Fluvac will be evaluated by the number and proportion of participants experiencing AEs by severity and relatedness to vaccination of the following five categories for all participants:

- A. Solicited local adverse events, including redness / erythema, swelling / induration, pain within 30 minutes of vaccination and over a 3-day period (Day 0-3) post-vaccination.
- B. Solicited systemic adverse events, including fever, fatigue, malaise, muscle aches, joint aches, chills, nausea, and headache within 30 minutes of vaccination and over a 3-day period (Days 0-3) post-vaccination.
- C. Unsolicited AEs occurring within 90 days post vaccination.
- D. SAEs occurring during the entire study period (Days 0-90).

Occurrences of all events will be reported and summarized according to event severity, as "any local AE", or "any systemic AE", and by relationship to administration of study product, as deemed by a blinded study clinician. Percentage of participants experiencing each reaction or event, or at least one reaction or event will be calculated along with two-sided exact 95% CIs. No statistical testing will be performed for unsolicited AEs; including SAEs. The percentage of participants with solicited AE and SAEs will be compared between vaccine and comparator groups and a two-sided p-value of 0.05 will be considered statistically significant.

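### Stopping rule 3 pauses vaccination automatically, but a grade 3 reaction that is not flu-like and needs no medical care has no reporting time before the Day 4–14 diary review

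*Protocol*

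**What the plan says.** Protocol section 9.3 makes the stopping rules automatic: "The occurrence of one or more of the following criteria will automatically pause or halt further vaccinations in the study". Rule 3 is met when "Ten or more subjects experience a grade 3 or greater reactogenicity event following vaccination that is suspected to be vaccine related". Rule 4 works in the same way for five subjects with the same grade 3 clinical abnormality, which may be a solicited reaction.

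Section 8.2 describes how reactogenicity is captured: "solicited local and systemic AEs will be assessed by study staff 30 minutes after vaccination then daily for three days by the participants". The diary comes back at the visit headed "Day 7(-3, +7 days) after Injection: Return the diary card", where "Study staff will review the participant diary card and interim history with the participant".

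The protocol sets a time for earlier contact in two cases. Sections 7.3 and 7.4.1 ask for prompt notice of an event that requires medical care. Section 7.6 asks participants with flu-like symptoms to attend within 48 hours. Other routes carry no time: the general request to report adverse events (4.1), the optional unscheduled visit (7.6) and reporting of unsolicited events at any time (8.3). Section 4.6.3 mentions upcoming telephone calls, but the only scheduled call is at Day 60 (4.1, 7.4.3). Expedited review (9.2) lists erythema or induration only at grade 4.

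On causality, section 8.2 says: "Investigators will not be required to assess causality of solicited adverse events if the onset is during the solicitation periods". Section 8.7 has a physician-investigator assess causality of adverse experiences in general, and section 11.4 summarises events "by relationship to administration of study product, as deemed by a blinded study clinician".

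**The concern.** An automatic rule acts only as fast as its count. Grade 3 does not imply medical care: in Appendix A, injection-site pain is grade 3 when it stops usual activities, and redness or swelling is grade 3 at 10 cm or more. A participant can follow every written instruction and still leave the site unaware of such a reaction until the diary visit. Meanwhile vaccination continues, and the tenth qualifying event may already have happened.

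There is also a wording point. Rule 3 counts events that someone suspects are due to the vaccine, while section 8.2 does not require that assessment for the class of event the rule mostly counts. The protocol does not say how an unassessed solicited reaction is tallied, or when any assessment is made.

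**Working it through.** **Inputs**
- Visit window: Day 7, −3 to +7 (section 7.4.1).
- Onset days: Days 1–3 under section 7.3, where the diary starts the day after injection; Days 0–3 under section 4.1 and Table 2. Both are carried below.
- 945 participants, 2:1; study duration of about one year (Protocol Summary); final visit at Day 90 (+7).
- Enrolment pace and grade 3 rate are not given. Pace is bounded from the study duration, and the rate is an assumed range. The nearest figure is section 2.4: severe events of any kind in 2/200 on vaccine and 1/100 on placebo.

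**1. Review window.** 7 − 3 = Day 4; 7 + 7 = Day 14.

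**2. Lag = visit day − onset day.** At a Day 7 visit:
- Days 1–3: 7 − 3 = 4 to 7 − 1 = 6 days, mean 5 if onsets are even.
- Days 0–3: 4 to 7 days, mean 5.5.
- Extremes of the window: 4 − 3 = 1 day to 14 − 1 = 13 days (14 with a Day 0 onset).

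**3. Slowest even pace that fits 365 days.** Enrolment lasts 365 − 90 = 275 or 365 − 97 = 268 days. 945/275 × 7 = 24.1 a week; 945/268 × 7 = 24.7 a week; midpoint 24.4.

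**4. Further vaccinations = pace × lag/7, if nobody reports early.**
- Shortest: 24.1 × 4/7 = 13.8, about 14.
- Longest: 24.7 × 6/7 = 21.2, about 21; with Day 0 onsets, 24.7 × 7/7 = 24.7, about 25.
- Mean: 24.4 × 5/7 = 17.4; with Day 0, 24.4 × 5.5/7 = 19.2.

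**5. A faster pace.** The Study Status page records 24 July 2017 to 31 March 2018, which is 250 days.
- If primary completion was the last Day 90 visit (assumption), enrolment took 250 − 90 = 160 or 250 − 97 = 153 days, which is 41.3–43.2 a week. That gives 41.3 × 4/7 = 23.6 to 43.2 × 6/7 = 37.0 people (43.2 with Day 0).
- If it was the last Day 21 visit (assumption), enrolment took 229 or 222 days, which is 28.9–29.8 a week. That gives 28.9 × 4/7 = 16.5 to 29.8 × 6/7 = 25.5 people (29.8 with Day 0).

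**6. Voluntary early reporting.** If a share f is reported the same day, the mean delay is (1 − f) × mean lag. At f = 0.5: 2.5 days, or 24.4 × 2.5/7 = 8.7 people (9.6 with Day 0). At f = 0.75: 1.25 days, or 4.4 people (4.8 with Day 0).

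**7. Extra grade 3 reactions = mean further vaccinations × rate**

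| Assumed rate | 17.4 people | 19.2 people |
|---|---|---|
| 1% | 0.17 | 0.19 |
| 2% | 0.35 | 0.38 |
| 5% | 0.87 | 0.96 |
| 10% | 1.7 | 1.9 |

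At the fastest pace with the longest Day 7 lag, 43 × 2% = 0.9.

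**8. Is the threshold reachable?** The rule does not separate arms, so X ~ Bin(945, p). P(X ≥ 10) is 0.02 at 0.5%, 0.47 at 1% and 0.99 at 2%. The tenth event is expected after 10/p people: 1,000 at 1%, 500 at 2%, 200 at 5% and 100 at 10%.

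**9. Calls under the fix.** 945 × 1% = 9.5; 945 × 2% = 18.9.

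**The case against.** **The class is narrow.** Reactions in the first 30 minutes are recorded by staff (8.10). Many systemic reactions would fall under the 48-hour flu-like request, and anything needing care is reported promptly. Participants are asked to report adverse events and may attend for any of them. All of this stands and is why the finding is limited to the remainder, but none of it puts a time on that remainder. A reader might infer that the site cannot learn of a grade 3 reaction before Day 4. The documents do not say that; they only leave early notice to the participant.

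**The material is incomplete.** A call instruction would naturally sit on the diary card or in the consent form, and neither was available. This stands: the point concerns the protocol text only.

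**The effect is small.** At 1–2% it is well under one reaction. Each person has one dose, symptoms are expected to clear in 1–3 days (2.6), rules 1 and 2 act on a single event, and sections 6.2 and 9.3 let others suspend the trial. At 1% the tenth event is expected at about the thousandth person, so little would be left to pause. This stands and sets the priority. The counterpoint is that the rule exists for a vaccine more reactogenic than expected. At 5–10% the tenth event is expected near person 200 or 100, with most of the trial still to be vaccinated.

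**Section 8.2 might seem to disable rule 3.** The documents do not support that. Causality is not required there, but it is not barred. The same section defines solicited events as common after, or associated with, vaccination, and the rule asks only for suspicion. Sections 8.7 and 11.4 both refer to a relationship assessment. What remains is an unresolved wording difference.

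**The section 9.3 line is not neutral.** If half of a 1% rate would otherwise be called unrelated (an assumption), counting every event moves the chance of reaching ten from 0.02 to 0.47. The direction stands, and the sponsor should accept it knowingly.

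**Conclusion.** The timing gap holds on the protocol text. For a grade 3 reaction that starts after the 30-minute check, is not flu-like and needs no care, nothing written requires the site to know before the Day 4–14 diary review, so the count behind an automatic pause can run days late.

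The size rests on visits at Day 7, an even pace of 24–25 a week and no early reporting. On those assumptions the lag costs about 14–21 further vaccinations (14–25 with Day 0 onsets). A faster pace raises this and voluntary reporting lowers it. The expected harm is about 0.2–0.4 extra grade 3 reactions at 1–2% and about 1–2 at 5–10%. The benefit is therefore modest and arises mainly if the vaccine proves more reactogenic than in the earlier trial.

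A reader might infer a serious lapse in participant protection, or a rule that cannot work. Neither follows: the single-event rules and the powers to suspend are intact, and the causality point needs clarification only. This is an optional improvement, worth making because it is cheap.

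**What to change.** - **Section 7.3 and the diary card:** tell participants to telephone the site on the day they record any grade 3 or greater reaction, whether or not they need care. Staff can say this when they explain the diary (4.6.3).
- **Confirmation:** a blinded physician-investigator confirms the grade promptly, by telephone where possible. This fits section 8.6, which already states: "An investigator who is a qualified physician, will evaluate all adverse experiences as to" severity. The event counts toward rule 3, and toward rule 4 where it is a solicited reaction, from that date.
- **Section 9.3, as a clarification:** solicited reactions with onset in the solicitation period count as suspected to be related for this tally.

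Thresholds, visits and the grading table stay as they are. The cost is one line in each of three places and about 9–19 calls at a 1–2% rate, each with a brief confirmation. The downside is that some unrelated symptoms may be counted, so a pause could come sooner. If the diary card or consent form already carries the call instruction, only the confirmation step and the section 9.3 line are needed.
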